ongoing activity that students can participate in until they leave or graduate from school. Girls participating in the SOC Arm (SKILLZ-Girl) are able to join any of the other clubs currently offered at their school (SOC Clubs).

Clubs have been operating in schools in Zambia since 2017 with the MOGE's consent as part of the Memorandum of Understanding (MOU) signed in 2010 (*see Appendix B*). The CLUB component is currently evolving to include a more formalized education component, and will be piloted in Zambia at the same time as this evaluation.

4. All girls who test positive for HIV (whether prior to the SKILLZ-Girl event, during the event or as part of their participation in SKILLZ-Club) are referred to **SKILLZ-Plus**, a clinic-based initiative which provides HIV-infected girls access to ongoing support through a 12-week curriculum. During follow-up in the SOC Club arm, study staff will refer any newly identified HIV-positive girls to SKILLZ-Plus. In addition, study staff will refer newly diagnosed girls aged 16 years from neighboring clinics to the SKILLZ-Plus intervention.

For girls who test positive for HIV, either through a:

1. school referral either at the event, during club participation, are identified during follow-up or with a previously known diagnosis or
2. clinical referral (newly diagnosed only)

In addition, all girls found to be HIV-positive at any point throughout the SKILLZ-Program will be provided with intensive counselling support. Coaches will facilitate a family visit to facilitate disclosure and work with CIDRZ networks to provide additional psycho-social support as needed on a case-by-case basis by the participant.

SKILLZ-Plus provides several additional features:

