Within SKILLZ-Girl and SKILLZ-Club, our study will examine the additional benefits of offering access to two new health service offerings that are expressly designed to overcome barriers to uptake especially difficult for adolescents to overcome—HIV self-testing (HIVST) kits and access to an expanded method mix for contraceptive methods. Referral for contraceptive and SRH services will be made to the PEPFAR-funded DREAMS Houses or youth corners at local government facilities which are located within close distance to all schools where the SKILLZ package will be implemented.

Our mixed-methods evaluation will assess the effects of the enhanced SKILLZ offering (SKILLZ-Girl Enhanced & SKILLZ Club programs) compared to the SOC SKILLZ offering of SKILLZ-Girl only. Although the SKILLZ Program (Enhanced or SOC pending school allocation) will be offered to all girls enrolled in Grade 10 at selected study secondary schools, only girls aged 16 and over at the commencement of SKILLZ-Girl will be enrolled into the research study.

We will examine outcomes for school girls aged 16 and over enrolled in Grade 10 at the start of the intervention in up to 16 schools where the SOC SKILLZ Package is offered, compared to outcomes in up to 16 schools where the enhanced SKILLZ-Package is offered, including HIVST, the availability of expanded contraceptive services and the SKILLZ-Club following completion of SKILLZ-Girl. Therefore, all schools will be preassigned prior to the intervention into the following 2 categories (see **Figure 3** in *Section 8 - Methodology* below).

1. **SOC:** SKILLZ-Girl → Club SOC
2. **ENHANCED:** SKILLZ-Girl enhanced → SKILLZ-Club

Our central hypothesis is that the additional offering of HIVST and contraceptive services in an enhanced SKILLZ-Girl combined with the SKILLZ-Club offering will increase HIV testing and contraceptive uptake and continuation.

In addition to SKILLZ-Girl and SKILLZ-Club, girls testing HIV-positive at any time during the study intervention period will be additionally offered to participate in the SKILLZ-Plus facility-based curriculum for HIV-infected adolescents. The effect of the SKILLZ-Plus curriculum will be tested using a SmartCare-derived matched (i.e., on clinic, age, ART start date and gender) population.

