Cluster randomized controlled trial: We will select up to 18 (2 pilot + 16 for full implementation) schools from the Urban District of Lusaka to receive the SKILLZ-Girl curriculum. Of the total (up to 18), half will be randomly allocated to host the standard SKILLZ-Girl curriculum, and the remaining half (e.g., up to eight) will be randomized to either enhanced SKILLZ-Club. Those schools randomized to standard SKILLZ Girl curriculum will only have access to SOC clubs. Those schools selected for enhanced SKILLZ Girl curriculum will offer SKILLZ Club. See **Figure 3** for study allocation flow.

Figure 3. School Selection Flow Chart

[figure not shown]
ONGOING REFERRAL TO COMMUNITY CARE FOR SERVICES

We anticipate that most of our evaluation cohort will not be HIV-infected. Thus, the retention to SRH analysis drives the sample size calculation of 351 girls using contraception at the end of two years, with, and risk ratio difference of 0.3 (30%) between the SOC and enhanced SKILLZ-Club schools. To realize the 351 needed to meet requirements for estimate sensitivity, we augment the initial sample size receiving the SKILLZ-Girl curriculum accounting conservatively for 25% uptake of SRH methods and multiplying by two to assess the difference within each SKILLZ-Girl model (phase 1) and accounting for attrition across the two years of follow-up (12.5%) resulting in a starting sample size of 3159 $((351/0.25) \times 2) \times 1.025$. **SKILLZ-CLUBS** will act as an extension to the SKILLZ-Girl curriculum enabling participants to seamlessly transition from the SKILLZ-Girl curriculum into the SKILLZ-Club. We anticipate minimal attrition (~15-20%). Participants will spend the majority of the study window in SKILLZ-Club and it is through the SKILLZ-Club affiliation that we will follow-up and ascertain outcomes for those enrolled longitudinally.

For the small minority of girls found to be HIV-infected across all schools where the study will be conducted, we will evaluate linkage to care and on treatment, VLS, and retention in care for a period of two years. These girls will be encouraged to continue on to the HIV positive-specific SKILLZ-Plus facility-based curriculum. We will quantitatively measure the impact of SKILLZ-Plus on linkage to care and treatment, retention and viral load at 6, 12, and 24 months after diagnosis (or since participant is identified by GRS as HIV+) using SmartCare data and compare to an existing matched cohort.

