Difference-in-difference model. The primary outcome is the probability of testing for HIV at any time during the period when SKILLZ is delivered through to 24 months after the final soccer event. The primary analysis for Aim 1 will follow a difference-in-difference (DID) effect between study arms. The outcome of interest will be regressed on an indicator of study arm assignment interacted with a dichotomous variable POST which indicates the outcome after the intervention is implemented; this differentiates baseline and end-line for each study arm, controls for any time dependent variables that might confound the effect, as well as any time-invariant observed or unobserved confounders that might differ between study arm schools. Because of this, the DID is robust to time-invariant unobservable confounders (e.g., school quality) and time trends (e.g., secular increase in testing). Our estimator relies on the assumption of common time trends across intervention and control in absence of the intervention, and of static population. Additionally, we control for baseline individual and school-level moderators that may be unbalanced at baseline after randomization. School-level controls include size, promotion rates, sex composition and repetition and dropout rates (available in the district education office) and individual girls' controls include age, grade, maternal education, HIV knowledge. Clustering by school will be accounted for by a generalized estimating equation approach. We will estimate intention-to-treat (ITT) by including all girls in the evaluation cohort assigned to each arm rather than all girls who actually participated in SKILLZ.

Individual-level matched cohort analysis for HIV-infected: The analysis will follow an individual ITT estimator among individuals found to be HIV-infected, who will then be matched (based on clinic, age, ART state date, and gender) to HIV-infected individuals in the SmartCare database. The outcomes are the proportion of enrolled HIV+ girls who linked to care, who are virally suppressed and retained in care at 6, 12, and 24 months after diagnosis of HIV+ (using national electronic HIV medical record data). We will conduct an ITT analysis for the logistic probability of being suppressed at 6, 12, and 24 months after HIV+ diagnosis, where girl is the unit of analysis. All data will be analyzed using STATA.

Process evaluation: This will involve quantitative and qualitative analyses:

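### The sampling section and the analysis plan start the clock for SKILLZ-Plus outcomes at different dates, and for girls with an earlier HIV diagnosis the analysis plan's landmarks can fall before they entered the programme

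*Combined protocol and SAP*

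**What the plan says.** **Who enters.** Section 4, item 4, gives two routes into SKILLZ-Plus. The school route covers girls who test positive at the event or in a club, and those who "are identified during follow-up or with a previously known diagnosis". The clinic route takes new diagnoses only. Later in Section 4, where the study arms are described, the offer is put differently: "girls testing HIV-positive at any time during the study intervention period will be additionally offered to participate in the SKILLZ-Plus" curriculum. Section 7, Aim 1(ii), defines the cohort as girls found to be HIV-positive in the course of SKILLZ-Girl or SKILLZ-Club who then enrol in SKILLZ-Plus. Section 8a assumes that the offer coincides with infection.

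**When the clock starts.** Section 8f (individual-level matched cohort analysis) takes as outcomes the proportions linked, virally suppressed and "retained in care at 6, 12, and 24 months after diagnosis of HIV" infection. It then models the probability of "being suppressed at 6, 12, and 24 months after HIV+ diagnosis, where girl is the unit of analysis". Section 8c says that linkage, retention and viral load will be measured "at 6, 12, and 24 months after diagnosis (or since participant is identified by GRS as HIV+) using SmartCare data". Section 8f does not repeat the alternative in brackets.

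**Comparators.** They come from SmartCare, matched on clinic, age, ART start date and gender (Sections 4 and 8f).

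**The concern.** For a girl first diagnosed by the programme, diagnosis and identification nearly coincide, so either origin gives about the same landmarks. For a girl who already knew her status, the two origins differ by the whole interval between her diagnosis and her contact with GRS. The unsettled rule therefore matters mainly for the known positives whom Section 4 admits.

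If the diagnosis date is used for such a girl, some or all of her results belong to care she received before SKILLZ-Plus. A viral load or pharmacy visit before entry cannot respond to the programme. If she was already in care, linkage was settled beforehand.

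The bias could run either way. Results from before entry dilute any true effect. On the other hand, SKILLZ-Plus is delivered at the clinic around routine visits, so known positives who join may be those who stayed in care, which would flatter the programme. With two origins on paper and no assignment rule, the choice could also be made after the data are seen.

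**Working it through.** The plan gives no figure to reproduce here. The check compares the sections and works out where the landmarks fall.

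**Inputs**
- Landmarks t = 6, 12 and 24 months (Sections 8c and 8f).
- Origin: diagnosis (Section 8f); diagnosis or GRS identification (Section 8c).
- D = months from diagnosis to SKILLZ-Plus entry. The documents do not give it; the values below are assumptions to show the range.
- L = months from GRS identification to SKILLZ-Plus entry. Also not given.

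**Origin at diagnosis (Section 8f).** The landmark falls t − D months after entry, and before entry when D > t.

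| D (assumed) | 6-month landmark | 12-month landmark | 24-month landmark |
|---|---|---|---|
| 3 | 6 − 3 = +3 | 12 − 3 = +9 | 24 − 3 = +21 |
| 9 | 6 − 9 = −3 | 12 − 9 = +3 | 24 − 9 = +15 |
| 18 | 6 − 18 = −12 | 12 − 18 = −6 | 24 − 18 = +6 |
| 36 | 6 − 36 = −30 | 12 − 36 = −24 | 24 − 36 = −12 |

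Values are months from entry; negative means before SKILLZ-Plus. The 6-month landmark is lost when D > 6, the 12-month when D > 12, and all three when D > 24. Even where a landmark stays positive, exposure at that point is shorter than its label says: at D = 9, the 12-month result reflects 3 months since entry.

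**Origin at identification (the Section 8c alternative).** The landmark falls t − L months after entry, whatever D is. None precedes entry as long as L is below 6 months.

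**Scale.** Section 8a expects about 98% of girls who test to be negative. With an average of 100 girls in each of 18 schools (Section 8c), 0.02 × 1,800 = 36 would test positive if all tested. With the target of 3,200 (Section 8d), 0.02 × 3,200 = 64. If 60% to 80% test, these become about 22 to 29 and 38 to 51. The figures show only that the group found by testing is small. They are not a base for the number affected: girls who already know they are positive may not test, and clinic referrals add an unstated number.

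**The case against.** The strongest reply is that Section 8c already deals with this. Its bracketed alternative reads most naturally as a provision for girls diagnosed before GRS met them, and under it no landmark depends on the diagnosis date. That is a fair reading of intent. A reader might infer that the plan counts every outcome from diagnosis alone; Section 8c shows that it does not. But the alternative has no rule for who receives it, and the section that specifies the analysis leaves it out.

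A second reply is that Section 4 describes referral to a service, whereas the analysed cohort is set by Aim 1(ii), which may exclude known positives. The documents are unclear here, but the Section 8c alternative has little purpose unless such girls are analysed.

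Other stronger inferences are not supported:
- **That the two entry routes contradict each other.** Different criteria for school and clinic referral are a stated choice, and the offer to girls testing positive during the study does not exclude others.
- **That the analysis cannot answer research question c.** That question concerns HIV-positive girls in general, not new diagnoses, and does not list linkage. Matching on ART start date also goes part of the way towards comparing girls with similar treatment histories.
- **That the effect would be diluted by a calculable amount.** This would need the previously diagnosed share, the distribution of D and a true effect, none of which is given.

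**Conclusion.** The point holds as an unreconciled time origin. Read literally, Section 8f places the 6-, 12- and 24-month outcomes before SKILLZ-Plus entry for girls diagnosed more than 6, 12 or 24 months earlier, and Section 8c offers a different origin without assigning it. The conclusion rests on known positives being in the analysed cohort, which Sections 4 and 8c imply but Aim 1(ii) does not settle. Neither the number of girls affected nor the direction of bias can be computed from the documents.

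The effect is confined to the matched-cohort analysis of HIV-positive girls. Section 8f names HIV testing as the primary outcome, and that is untouched. The matched cohort is not trivial, however: Section 8c speaks of primary endpoints in Aim 1(ii), and this is the planned comparison for SKILLZ-Plus. It should be fixed before analysis.

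**What to change.** 1. In Sections 8c and 8f, define one time zero for every girl: the date GRS identifies her as HIV-positive, or the date she is referred to SKILLZ-Plus. Choose one, record it on the study forms, and count 6, 12 and 24 months from it.
2. Give each SmartCare comparator an index date at the same time since ART start as her matched girl, and require the comparator to be under observation on that date. SmartCare comparators have no GRS identification date, so moving the girls' origin alone would misalign the groups. State separately how the index date is set when a girl has not started ART at time zero.
3. Restrict the linkage outcome to girls newly diagnosed in the study or referred newly diagnosed from a clinic.
4. Report suppression and retention by newly versus previously diagnosed status, as a descriptive split.
5. Make Section 4 (both places), Aim 1(ii) and Section 8a agree on whether known positives are in the analysed cohort, and say whether clinic referrals are.

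The cost is mainly wording. Section 8e lists ART initiation, visit and laboratory data in SmartCare, and the baseline survey in Section 8d asks about HIV status. The downsides are fewer girls in the linkage outcome, thin subgroups, and later landmarks for previously diagnosed girls, some of whom may not reach 24 months before the data are extracted.

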GRS has shown that soccer-based interventions combined with strong school and community partnerships and referral networks can change behaviors and make a significant impact on the health of young people.⁵³ In 2009 in South Africa, GRS piloted the SKILLZ-Girl program which addresses the unique needs of young women and adolescent girls. This program was then scaled in South Africa and expanded further into 13 countries in SSA. A recent evaluation of the SKILLZ-Girl program showed that participants significantly improved their knowledge and attitudes surrounding HIV risk for young women, negotiation skills, and sense of self-efficacy. In fact, 68.5% of girls that participated in the SKILLZ-Girl program underwent testing for HIV at the conclusion of the school-based curriculum.⁵⁴ Although SKILLZ-Girl has now served over 26,000 girls in 14 countries, it has never been rigorously evaluated for cost effectiveness and effectiveness.

6. Research questions

Our mixed-methods evaluation aims to assess the effect of the enhanced SKILLZ- girl on HIV testing and SRH related prevention services uptake (Aim 1), the effect of SKILLZ-Plus on HIV retention to care and VLS amongst HIV-infected girls (Aim 2) and identify mediating pathways and moderating factors leading to observed effects (Aim 3). Aim 3 will also assess the cost-effectiveness of the SKILLZ Package.

Our research questions are thus:

- a. What is the impact of enhanced SKILLZ-Girl vs regular SKILL-girl curriculum on HIV testing uptake among adolescent girls (aged 16 and over) over a 24-month period?
- b. What is the impact of enhanced SKILLZ-Club on HIV testing uptake among adolescent girls (aged 16 and over) over a 24-month period?
- c. Among HIV-positive adolescent girls, what is the impact of the SKILLZ-Plus intervention on:
 - a. retention in care and treatment at 6, 12, and 24 months
 - b. viral load suppression at 12 months?

- d. What specific barriers to access to services do the SKILLZ interventions (SKILLZ Girl, enhanced SKILLZ-girl, SKILLZ-Club & Plus) overcome?
- e. What are the mediators of the observed effects?
- f. What are the moderators of the observed effects?
- g. To what degree was the intervention implemented per protocol (fidelity)?
- h. What is the short- and long-term cost-effectiveness of the SKILLZ Package intervention?

7. Research aim(s)/General Objective and Specific Objectives

Aim 1: Assess the impact of SKILLZ over two years on:

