- (i) (a) **HIV testing** and (b) SRH-related prevention services uptake among adolescent girls aged 16-19 in up to 9 intervention schools (with enhanced HIVST, PrEP, and contraceptive method offerings) compared to up to 9 control schools using a quasi-experimental difference-in-difference approach; and
- (ii) **linkage to care and treatment, and viral load suppression and retention at 6, 12, and 24 months** through a cohort model using pre-existing SmartCare data on HIV+ individuals in care to match to adolescent girls aged 16 and over from the same district (Lusaka) who are identified to be HIV+ at any time during SKILLZ Girl or SKILLZ Club participation and enrolled in SKILLZ-Plus.

This will be achieved by i) using a quasi-experimental difference-in-difference approach that compares girls aged 16 and over in 9 SKILLZ control schools compared to 9 schools where enhanced SKILLZ will be delivered with the enhanced HIVST and a variety of contraceptive method offerings; and ii) through a cohort model using pre-existing SmartCare data on HIV+ individuals in care to match to adolescent girls aged 16 and over from the same district (Lusaka) who are identified to be HIV+ at any time during SKILLZ-Girl or SKILLZ-Club participation.

Aim 2: Examine how the intervention works including lessons learned for future implementation by

- (i) conducting a process evaluation to identify mediators, predictors, and barriers to uptake of the SKILLZ-Girl, Club, and Plus curricula both quantitatively through mediation and moderation analyses and qualitatively through a sequential explanatory approach using focus groups discussions, interviews and observation with coaches and girls; and by
- (ii) monitoring fidelity

Aim 3: Estimate the short- and long-term cost-effectiveness and return on investment of the SKILLZ Girl, Club, and Plus curricula for improving health outcomes for adolescent girls.

8. Methodology

a. Study design

We will conduct a mixed-methods evaluation of the SKILLZ intervention using the following approaches:

A **quasi-experimental cohort** of school-aged 16-year old and over females to be followed for a two-year period will be evaluated with a difference-in-difference (DID) approach to estimate HIV testing uptake and sexual/reproductive health services use. Primary and secondary outcomes will be measured at several

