timepoints longitudinally across up to 9 schools offering the enhanced SKILLZ-Girl and SKILLZ-Clubs program and up to 9 schools offering the “standard of care” (SOC) SKILLZ-Girl and SOC Clubs (see Figure 3). Recruitment will take 12 months on a rolling basis. The order in which schools will be selected will be random. Participants will be clustered at the school-level; we will enroll all girls aged 16-years at the commencement of SKILLZ-Girl and in Grade 10 from each participating school.

[figure not shown]
All enrolled girls will be followed over the two-year time period to assess SRH service uptake, including HIV testing. It is estimated that the majority (~98%) of girls testing for HIV will likely be HIV-negative, based on estimates from programmatic GRS data. While HIV-positive girls will continue to participate in the school-based SKILLZ-Girl and Clubs activities and followed for SRH use, they will also be offered contemporaneous enrollment into SKILLZ-Plus upon infection; retention in care and Viral Load Suppression (VLS) at 6, 12, and 24 months will be measured for this subset. See **Figure 2** for details of enrolment flow.

Process evaluation: We will conduct a process evaluation to better understand the casual pathways and effect mediators and moderators using mixed methods approaches, including supplemental qualitative data collection. To investigate reasons why the program components (SKILLZ-Girl, Club & Plus) might fail or succeed in different schools or communities and assess intervention effect mediators and moderators for HIV testing and contraceptive use uptake we will use a mixed methods approach involving: (1) quantitative analyses of baseline survey data for testing how variables can moderate the observed impact of the intervention, and (2) qualitative data collected from a subset of SKILLZ participants in the evaluation cohort and their coaches to further understand potential mediating pathways outlined in Figure 1.

Fidelity monitoring: We will also include measures to monitor fidelity of the intervention implementation, including receptivity to and understanding of the intervention amongst participants, the perceived appropriateness and relevancy of the intervention for adolescent girls in school, and the extent to which the intervention was delivered per protocol in different communities and schools.

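### The SmartCare matched contrast is labelled as the effect of SKILLZ-Plus, but it estimates SKILLZ-Plus bundled with the school programme, and nothing in the plan separates the two

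*Combined protocol and SAP*

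**What the plan says.** Three places present the matched contrast as the effect of SKILLZ-Plus:

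- Section 4, after the list of arms: "The effect of the SKILLZ-Plus curriculum will be tested using a SmartCare-derived matched (i.e., on clinic, age, ART start date and gender) population".
- Section 6, research question c: "Among HIV-positive adolescent girls, what is the impact of the SKILLZ-Plus intervention on" retention and viral load suppression.
- Section 8c: "We will quantitatively measure the impact of SKILLZ-Plus on linkage to care and treatment, retention and viral load at 6, 12, and 24 months".

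Other places define who is exposed and to what:

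- Section 7, Aim 1(ii), forms the cohort from girls "who are identified to be HIV+ at any time during SKILLZ Girl or SKILLZ Club participation and enrolled in SKILLZ-Plus".
- Section 8a: "HIV-positive girls will continue to participate in the school-based SKILLZ-Girl and Clubs activities", and "they will also be offered contemporaneous enrollment into SKILLZ-Plus upon infection". The two exposures run side by side.
- Section 4, item 4, extends SKILLZ-Plus to control schools: "During follow-up in the SOC Club arm, study staff will refer any newly identified HIV-positive girls to SKILLZ-Plus". It also admits a route outside the study schools: "study staff will refer newly diagnosed girls aged 16 years from neighboring clinics to the SKILLZ-Plus intervention".

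Section 8f repeats the four matching variables and specifies an ITT analysis of girls found to be HIV-infected. It describes no term, restriction or stratum for school-programme exposure in either group.

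**The concern.** The question asked and the contrast planned do not match. A difference in linkage, retention or suppression between these girls and SmartCare patients could come from SKILLZ-Plus, from the school programme, or from both. The plan would report it as SKILLZ-Plus.

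The plan itself expects the other components to act on the same outcomes. Section 1c sets out to measure the effect of the enhanced package, and of the clubs, on retention in care. Section 3b expects the clubs to improve retention. It also names empowerment and reduced stigma both as effects of the school programme and as effects of SKILLZ-Plus. On the plan's own hypotheses, then, a non-zero contrast could appear even if SKILLZ-Plus did nothing.

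At stake is a decision to scale up SKILLZ-Plus, a separate clinic-based curriculum, on evidence that does not isolate it.

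**Working it through.** The documents give no sample size, effect size or power for this contrast, so there is no stated figure to reproduce.

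**1. What each group receives**

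| Group | School programme | SKILLZ-Plus |
|---|---|---|
| HIV-positive girls, SOC schools | Standard SKILLZ-Girl | Offered |
| HIV-positive girls, enhanced schools | Enhanced SKILLZ-Girl and SKILLZ-Club | Offered |
| SmartCare comparators | Not stated, not matched, not restricted | No offer described |

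SOC schools versus enhanced schools compares school programmes, with SKILLZ-Plus offered on both sides. Either school group versus SmartCare varies SKILLZ-Plus and, to an unknown degree, the school programme together. No planned contrast varies SKILLZ-Plus alone. The clinic-referred girls come closest, but Aim 1(ii) leaves them out.

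**2. Size of the misattribution (illustration)**

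Inputs:
- Control retention of 50% at two years. Section 5 reports that almost half of HIV-infected adolescents who know their status leave care within two years of starting ART.
- School-programme risk ratio R on HIV-care retention of 1.1 to 1.3. This is an assumption; the documents give no such value.
- SKILLZ-Plus has no effect, and the comparators had no benefit from the school programme. Both are assumptions made for the illustration.
- Share of girls who benefit, s: 0.5 if only enhanced-school girls do, 1 if all do.

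Excess = 0.50 × (R − 1) × s

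| R | s = 0.5 | s = 1 |
|---|---|---|
| 1.1 | 2.5 points | 5 points |
| 1.2 | 5 points | 10 points |
| 1.3 | 7.5 points | 15 points |

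**3. How many girls**

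Section 8a puts about 98% of girls who test as HIV-negative, so about 2% of testers are positive. Section 8c expects testing uptake of 60% (control) and 80% (intervention).

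- 18 schools × 100 girls = 1,800: SOC 900 × 0.60 × 0.02 = 10.8; enhanced 900 × 0.80 × 0.02 = 14.4; total about 25.
- Survey target of 3,200 (section 8d): SOC 1,600 × 0.60 × 0.02 = 19.2; enhanced 1,600 × 0.80 × 0.02 = 25.6; total about 45.

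Girls with previously known diagnoses would add an unstated number.

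**4. Chance that the excess is declared significant**

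Assume 1:1 matching (the documents give no ratio) and a two-sided z test at 5%, treating the groups as independent:

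SE = √[(p₀(1−p₀) + p₁(1−p₁))/n], and the probability is Φ(d/SE − 1.96) + Φ(−d/SE − 1.96), with p₀ = 0.50 and d = p₁ − p₀.

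| n per group | d = 7.5 points | d = 15 points |
|---|---|---|
| 25 | SE 0.141, 8% | SE 0.138, 19% |
| 45 | SE 0.105, 11% | SE 0.103, 31% |

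These compare with a nominal 5% if the contrast isolated a null SKILLZ-Plus effect.

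**The case against.** The strongest reply is that the plan already frames this as a package effect. The lead-in to Aim 1 speaks of the impact of SKILLZ, the end of section 4 of the Package's impact on testing and what follows in care, and section 9 of the Package with its three components, listing suppression and retention among the outcomes. Read that way, the contrast can address the formal aim, subject to other confounding. This stands, and it makes the fix easy. It does not remove the defect, because research question c and the operative sentences in sections 4 and 8c name SKILLZ-Plus alone.

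A reader might infer more than the documents support:

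- **That the SmartCare comparators had no school programme.** This is not stated. Section 1c says the standard curriculum already runs at most Lusaka secondary schools, and no exclusion for earlier exposure is given. Earlier exposure would shrink the SKILLZ-Girl part of the excess. Because it is unknown, it still prevents SKILLZ-Plus from being isolated.
- **That every SKILLZ-Plus girl receives all three components.** SOC-school girls receive two, and clinic-referred girls enter without the study's school route.
- **That section 8c supplies the risk ratio.** Its 30% difference concerns contraceptive use between enhanced and SOC schools. It is not evidence about HIV-care retention and cannot anchor the scenario in which all girls benefit.
- **That 2% applies to every enrolled girl.** That would give 36 or 64 girls and larger rejection probabilities, but the 2% refers to girls who test.

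It is also fair that this aim concerns a small minority and not the primary outcome, HIV testing.

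**Conclusion.** The concern holds in this form: as planned, the matched contrast estimates a bundle, either SKILLZ-Plus with SKILLZ-Girl or SKILLZ-Plus with enhanced SKILLZ-Girl and Club. It therefore cannot answer research question c as worded. That conclusion rests on the text alone.

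The size is not known. The illustrated range of 2.5 to 15 points depends on an assumed risk ratio and on comparators without school-programme benefit; it would be zero if the school programme did not affect HIV care. With 25 to 45 girls per group, such an excess would be significant about 8% to 31% of the time across the 7.5-point and 15-point cases. An unsupported claim from the point estimate is thus a risk as well as a false-positive test. The documents do not support saying that the comparators were wholly unexposed, or that any observed benefit must come from the school programme.

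**What to change.** In section 4, research question c, section 8c and section 8f, restate the contrast as the SKILLZ school programme plus SKILLZ-Plus versus routine SmartCare care. This agrees with the Aim 1 lead-in, the end of section 4 and section 9. State that no conclusion will be drawn about SKILLZ-Plus alone.

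Report the results separately for girls from SOC and enhanced schools, as description only. The strata are very small: about 11 and 14 girls from 1,800, or 19 and 26 from 3,200. They cannot separate the components by test.

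Optionally, where records and consent allow, describe the comparators' earlier SKILLZ exposure, and describe the clinic-referred SKILLZ-Plus girls separately. The latter are newly diagnosed only, their number is not stated, and they too may have had SKILLZ-Girl earlier, so they would not give a clean estimate either.

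The relabelling and the stratified table need wording changes and data already due to be collected. The downside is a narrower claim on a non-primary aim. Only the optional steps may need further records or consent.
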